- c) Surgical technique, to ensure a balance between hernia repairs where the prosthetic bridges the fascial defect versus reinforces a primary fascial closure*

Patients will be enrolled only once.

Patients will undergo daily evaluations during their index hospitalization. Follow-up will consist of evaluations by the investigator-surgeon before and at 1 month after surgery. The study team will perform follow-up evaluations at 3, 6, 12, 18, and 24 months after surgery or until the patient's hernia recurs. (Table 1) Due to the scheduling challenges involved, we will allow for a two-week window around the patients' targeted post-operative evaluation times. Patients will be followed for a total of 24 months since there is good evidence that the majority of hernia recurrences will take place within the first 18-24 months after surgery. [19, 20, 40, 41] Each evaluation will include a brief clinical examination, laboratory analyses, (complete cell count and differential, serum electrolytes, creatinine, urea nitrogen, albumin, prealbumin, C-reactive protein, Hgb A1c, liver function tests, urinalysis), anterior and lateral photographs of the abdomen, and ultrasound examinations of the anterior abdominal wall. During the scheduled visits wherein blood draws will occur, plasma will be banked for possible future research, considering the future potential of using antibodies as biomarkers. Evaluations of patient well-being, including a visual pain survey, Activities Assessment Score, and SF36 and HerQLes quality-of-life questionnaires (Appendices 1-4) will be performed at enrollment and 1, 6, 12 and 24 months following surgery. In addition, this panel of well-being assessments will also be administered when a patient develops a wound occurrence and/or hernia recurrence. An abdominal CT scan with intravenous contrast and volumetric analysis of the hernia will be obtained before surgery and 24 months after the hernia repair or when the patient's hernia recurs. The patient-related factors of gender, ethnicity, age, body-mass index (BMI, with obesity defined as a BMI \geq 30), chronic obstructive pulmonary disease, cough, constipation, prostatism, diabetes mellitus, glucocorticoid therapy, chronic immunosuppression, smoking status (current activity and pack-years), location of the hernia and abdominal surgery history (including prior ventral or inguinal hernia repairs) will be recorded. Perioperative factors including the patient's ASA score, size of the fascial defect (area in cm² = craniocaudal x transverse dimensions in cm), use of component separation repair techniques, duration of the operation, estimated blood loss, blood transfusion, maximum and minimum body temperature, maximum and minimum systolic blood pressure, vasopressor administration, perioperative antibiotics (including antibiotic regimen, timing of first dose and duration of therapy), postoperative complications, hospital length of stay, total hospital and professional charges and mortality will also be recorded.

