
Clinical trial item or procedure	Screen / Initiation	Month 1	Month 3	Month 6	Month 12	Month 18	Month 24
history, physical exam & consent	X						
brief clinical evaluation		X	X	X	X	X	X
pain, activity & QoL assessments	X	X		X	X		X
clinical photographs	X	X	X	X	X	X	X
chemistry panel	X		X		X		X
CBC	X		X		X		X
PT/PTT	X						
liver function tests	X		X		X		X
albumin, prealbumin & CRP	X		X	X	X		X
urinalysis	X						
urine pregnancy	X						
hepatitis panel	X						
ECG	X						
chest x-ray	X						
abdominopelvic CT	X						X
abdominal ultrasound				X	X	X	X
patient expenses reimbursement			X	X	X	X	X

Table 1. Clinical trial protocol for comparing a permanent, synthetic prosthetic (Ventralight) versus a biologic prosthetic (Strattice®) for repair of a complex ventral hernia.

Before anesthesia is induced, measures to reduce the patient's perioperative risks for deep venous thrombosis/pulmonary embolism and gastrointestinal ulceration will be instituted according to institutional, risk-reduction protocols.

When anesthesia is induced, a first-generation cephalosporin will be given intravenously within thirty (30) minutes, prior to the incision, unless the patient has a clinically significant allergy to penicillin, in which case either clindamycin or vancomycin will be substituted. An alternative antibiotic can be given if needed to provide appropriate prophylaxis for patients with previous abdominal wound infections. Ceftriaxone and clindamycin will be given to patients whose procedure is expected to involve repair of the large intestine, unless the patient has a clinically significant allergy to penicillin, in which case either ciprofloxacin or ertapenem will be substituted for the cephalosporin. Quantitative wound cultures will be obtained in those patients with perioperatively identified wound contamination specific to the source, e.g., colostomy, infected ventral hernia mesh, incidental enterotomy, etc. For example, duplicate culture swab samples will be obtained from infected prosthetic mesh and abscesses, whereas duplicate tissue biopsies will be obtained from chronic wounds and fistula tracts.

Surgical techniques. The complex ventral hernias will be repaired according to one of two standardized techniques with the randomly selected prosthetic either bridging the fascial defect with mesh versus reinforcing a reconstituted linea alba.

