To evaluate perioperative pain we will use the visual analog scale (VAS) and quality of life using the Rand Short Form 36 (SF36), Activities Assessment Scale (AAS) and HerQLes questionnaires. The VAS and SF36 have been used to evaluate pain and quality of life outcomes in several studies of ventral hernia patients over the past several years. [7-10] Using these instruments will facilitate comparison of our results with those of other investigators. Importantly, the AAS and HerQLes quality of life tools were specifically designed and have been prospectively validated for use in patients undergoing ventral hernia repair. [11-13]

Data and Safety Monitoring Plan

Review of Safety Information. The PI, Designated Safety Officer and Internal Review Committee (IRC) will review safety data on an ongoing basis. The IRC will be composed of the PI, specialists in Infectious Diseases, Critical Care Medicine, Plastic Surgery and Biostatistics. The Designated Safety Officer will be a nurse or

research assistant with experience in clinical trial operations and safety. The IRC will prepare study data reports for review by the Data and Safety Monitoring Board.

An independent Data and Safety Monitoring Board (DSMB) will review safety data on an ongoing basis. The DSMB will be comprised of UCSF faculty and will be independent of the study team. The composition of the DSMB, as well as the schedule of activities will be made available to the NIDDK for its review. All DSMB members will review the protocol and ensure its understanding. In addition, all DSMB members will be presented with the DSMB charter and will sign a conflict of interest form.

Study Stopping Rules.

Enrollment and initiation of study treatment may be suspended at any time if any of these reviews conclude that there are significant safety concerns. If the trial is put on hold, all screening, enrollment, and initiation of any new study subjects will cease pending DSMB review.

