Study Comparing the Efficacy, Safety, and Cost of a Permanent, Synthetic Prosthetic Versus a Biologic Prosthetic in the One-stage Repair of Ventral Hernias in Clean and Contaminated Wounds.

NCT02041494

Document Date: July 23, 2014

STATISTICAL ANALYSIS PLAN

Data Analysis. The primary efficacy endpoint is the ventral hernia recurrence rate between the two treatment groups. Secondary endpoints will consist of comparisons of wound occurrences, perioperative complications, hospital length of stay, total hospital charges, pain, and quality of life. Continuous endpoints of hospital length of stay, total hospital charges, pain, and quality of life will be compared by the Mann-Whitney *U* test. The binary variables—wound infection, and perioperative complications—will be compared using Fisher's exact test. The cumulative percentages of patients with recurrences over time will be calculated and compared by using Kaplan-Meier curves and log-rank tests. We will investigate subgroup effects by comparing the size of the fascial defect (area in cm^2), patient co-morbidities, and clean versus contaminated wounds. All statistical tests will be two-sided. The primary analysis will be performed on an intention-to-treat basis for which patients will remain in their assigned group, even if during the procedure the surgeon judged the patient not to be suitable for the prosthetic or technique assigned. In addition a per-protocol analysis will also be performed for which patients with major protocol violations will be excluded.

Power Analysis: Overall, ventral hernia repairs recur with an estimated frequency of approximately 40%. However, conventional wisdom recognizes that wound contamination potentially doubles the risk of hernia recurrence. Therefore, we performed separate power analyses for hernia repairs under clean versus contaminated wound conditions that were informed by the medical literature and clinical studies we have conducted at UCSF.

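### Study-team visits end at hernia recurrence, but the pain and quality-of-life schedule runs to month 24 with no stop clause. If the questionnaires stop too, later scores are lost through the primary outcome and unequally between arms.

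*Protocol*

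**What the plan says.** The Protocol's General study design section handles recurrence differently for different assessments.

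- Visits: "The study team will perform follow-up evaluations at 3, 6, 12, 18, and 24 months after surgery or until the patient's hernia recurs". This sentence refers to Table 1.
- Overall follow-up: "Patients will be followed for a total of 24 months", with no exception for recurrence.
- Pain scale, Activities Assessment Scale, SF36 and HerQLes: these "will be performed at enrollment and 1, 6, 12 and 24 months following surgery". No stop at recurrence is stated.
- Extra panel: "this panel of well-being assessments will also be administered when a patient develops a wound occurrence and/or hernia recurrence".
- Abdominal CT after surgery: "24 months after the hernia repair or when the patient's hernia recurs".

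The Table 1 row "pain, activity & QoL assessments" is marked at screening and months 1, 6, 12 and 24, with no footnote on recurrence.

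The SAP (Data Analysis) lists pain and quality of life as secondary endpoints. Its whole analysis of them is one sentence: "Continuous endpoints of hospital length of stay, total hospital charges, pain, and quality of life will be compared by the Mann-Whitney" U test. It names no time point, does not say what happens when a score is absent after recurrence, gives no role to the panel taken at recurrence, and makes no use of the enrolment score.

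**The concern.** The questionnaires due at months 6, 12 and 24 coincide with study-team visits. If those visits end at recurrence, the questionnaires may end with them. Two people could each follow the Protocol faithfully and collect different data.

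Scores lost in this way would not be lost at random. They would be lost through the primary outcome, which the SAP (Power Analysis) assumes is twice as frequent with the biologic. A month-24 test on the scores that exist would then compare mostly recurrence-free patients, selected to a different degree in each arm. If one prosthetic improves quality of life because it prevents recurrence, such a test leaves out many of the patients in whom the difference would appear. Scores never collected cannot be recovered later.

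**Working it through.** **Inputs (SAP, Power Analysis and Table 2).** Recurrence with biologic v synthetic is 40% v 20% in clean wounds and 60% v 30% in contaminated wounds. The sample is 80 and 40 patients per group, two-sided 0.05, 80% power. Dropout is below 5%.

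**The plan's own figures.** With unpooled variance, n = (1.96 + 0.8416)² × [p₁(1−p₁) + p₂(1−p₂)] / (p₁−p₂)².
- Clean: 7.849 × 0.40 / 0.04 = 78.5, so 79.
- Contaminated: 7.849 × 0.45 / 0.09 = 39.2, so 40.

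The pooled form gives 82 and 42. The stated 80 and 40 are reproduced, and 240 / 0.96 = 250 fits the stated dropout.

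**Assumptions.** The planning rates are read as 24-month rates (the SAP gives no horizon). The mix is 2:1 clean to contaminated, from Table 2. There is no other dropout. A recurrence is found at the next scheduled visit, and the visit that finds it still yields a score.

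**Recurrence by month 24.** Biologic: (2/3)(0.40) + (1/3)(0.60) = 46.7%. Synthetic: (2/3)(0.20) + (1/3)(0.30) = 23.3%.

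**Month-24 scores if questionnaires stop.** A score exists if there is no recurrence by month 18. Under constant hazard, the recurrence-free share at month t is (1−p)^(t/24) in each wound stratum.
- Biologic: (2/3)(0.6^0.75) + (1/3)(0.4^0.75) = (2/3)(0.682) + (1/3)(0.503) = 62.2%.
- Synthetic: (2/3)(0.8^0.75) + (1/3)(0.7^0.75) = (2/3)(0.846) + (1/3)(0.765) = 81.9%.

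Per 120 patients in each arm, about 45 v 22 would have no month-24 score.

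**Other timings.** The Weibull rows use exponent (t/24)^k. The late-detection rows assume that a share of the recurrences arising by month 18 is found only at month 24. For half, this gives 1 − 0.5 × 0.378 = 81% and 1 − 0.5 × 0.181 = 91%.

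| Score available | Biologic | Synthetic |
|---|---|---|
| Month 24, constant hazard | 62.2% | 81.9% |
| Month 24, Weibull k = 0.5 | 57.9% | 79.4% |
| Month 24, Weibull k = 1.5 | 66.2% | 84.1% |
| Month 24, every recurrence found earlier | 53.3% | 76.7% |
| Month 24, 25% found only at month 24 | 72% | 86% |
| Month 24, 50% found only at month 24 | 81% | 91% |
| Month 12, constant hazard | 85.2% | 93.5% |
| Month 6, constant hazard | 92.3% | 96.7% |

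A further 5% dropout in each arm changes the first row to 59.1% v 77.8%.

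**What a test on available scores would keep.** Suppose every recurrence costs the same amount d, still present at month 24, and the prosthetic has no other effect. These are assumptions; the documents give no such figure. The full difference is (0.467 − 0.233)d = 0.233d. Among patients with scores, the recurrence shares are (0.467 − 0.378)/0.622 = 0.143 and (0.233 − 0.181)/0.819 = 0.064. The difference is 0.079d, which is 34% of the full one (19-45% across Weibull shapes 0.5 to 1.5). If 25% or 50% of recurrences are found late, 61% or 79% is kept. If every recurrence is found before month 24, nothing is kept.

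**How old the recurrence panel would be.** Under constant hazard, of the 45.3 v 21.7 patients without a month-24 score, 32.8 v 14.9 (72% v 69%) would have had their recurrence panel by month 12, at least a year earlier.

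**The case against.** The strongest objection is that the loss may never occur, and part of the text points that way. The questionnaire sentence and Table 1 include month 24 without exception. The panel at recurrence is introduced as an addition, not a substitute. The CT sentence shows that the authors wrote a recurrence clause where they wanted one. All of this stands, so the loss is conditional. It does not settle the matter, because the visit sentence with the stop clause itself refers to Table 1.

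A second objection also stands. Detection at the next visit is only one possibility. Table 1 shows no ultrasound at month 3 and no CT between surgery and month 24, although the General study design text lists ultrasound at each evaluation. A defect seen only on imaging counts as a recurrence. Late detection shrinks the loss, and month 24 is the worst time point.

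A reader might infer that the quality-of-life comparison is bound to lose most of any recurrence-related benefit. The documents do not support that: only one of two open readings produces the loss, and the retained share ranges from none to about 79% with timing and detection. Nor is the unadjusted Mann-Whitney test biased for ignoring the enrolment score; it is only less precise.

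Finally, these are secondary endpoints. Month-1 scores are little affected. So is pain, if it is meant only as perioperative, which is how the Protocol introduces the pain scale.

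**Conclusion.** The point holds in a conditional form. The Protocol contradicts itself on whether patients are still assessed after recurrence, and the SAP does not resolve it. If questionnaires stop with the visits, month-24 availability is about 62% v 82% on the base assumptions and 53-66% v 77-84% across timing assumptions. It could reach about 81% v 91% if half of the recurrences by month 18 are found only at month 24. At month 12 it is about 85% v 94%, and at month 6 about 92% v 97%. A test on available scores could then lose part, possibly most, of a benefit that acts through preventing recurrence. If questionnaires continue, that loss disappears; what remains is an unnamed time point and an unstated use of the recurrence panel. The time-to-recurrence analysis is untouched. The change should be made, but the trial's main conclusion does not depend on it.

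**What to change.** 1. Reconcile the Protocol passages by stating that the pain, activity and quality-of-life questionnaires continue at the remaining 6-, 12- and 24-month time points after recurrence in all randomised patients, by remote contact where there is no visit. On the next-visit detection assumption, the cost per 120 patients in each arm is about 45 v 22 (biologic v synthetic) extra questionnaires at month 24, 18 v 8 at month 12 and 9 v 4 at month 6.
2. In the SAP, replace the unadjusted Mann-Whitney test for these scores with a comparison at named time points adjusted for the enrolment score already collected (rank ANCOVA or a mixed model). This gains precision and does not correct a bias. For a correlation r between enrolment and later score, the variance is multiplied by 1 − r²: 0.91, 0.75 and 0.51 at assumed r of 0.3, 0.5 and 0.7. It needs only SAP wording.
3. Where a later score is still missing, use the recurrence panel in a stated sensitivity analysis and show results with and without it, because the score at recurrence may not represent the later state. Without item 1, a mixed model that includes the panel may recover part of the comparison, but only under a missing-at-random assumption.

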Study Comparing the Efficacy, Safety, and Cost of a Permanent, Synthetic Prosthetic Versus a Biologic Prosthetic in the One-stage Repair of Ventral Hernias in Clean and Contaminated Wounds.

NCT02041494

Document Date: July 23, 2014

STUDY PROTOCOL. The specific hypothesis driving the research application is that the use of a permanent synthetic prosthetic for the one-stage repair of complex ventral hernias will result in superior outcomes compared to a biologic prosthetic.

General study design. We propose a prospective, randomized, single-blind study in 330 patients with complex ventral hernias. A permanent synthetic prosthetic will be compared to a biologic prosthetic for clinical superiority. The primary endpoint is ventral hernia recurrence rate.

Eligible patients will be randomized to undergo open ventral hernia repair using either a permanent synthetic or a biologic prosthetic. Patients will be randomized while in the operating room using a technique of stratified randomization with permuted blocks to insure a balance between the two treatment groups at study entry. Patients assigned the synthetic code will be treated using the permanent synthetic prosthetic (Ventralight®, Bard, Murray Hill, NJ), whereas those patients assigned the biologic code will be treated with the biologic prosthetic (Strattice®, LifeCell Corp., Branchburg, N.J.). The selection of the synthetic and biologic prosthetics was based on a combination of established clinical experience and our best analysis of the available preclinical data. [33-39] Ventralight is a composite product that combines a synthetic mesh with a proven absorbable hydrogel barrier to minimize tissue attachment (adhesions) to the mesh. Strattice is a non-crosslinked, terminally sterilized, porcine dermal product recently introduced in 2007. While there is limited human data available, a multi-institutional trial evaluating its outcomes during the repair of infected and contaminated hernias was recently published. [6] Prior to the random assignment to receive either a permanent synthetic or a biologic prosthetic, patients will be stratified according to 3 factors;

- a) Charlson Index score, to ensure a balance of severity in chronic illnesses of the two patient groups;*
- b) Wound contamination, to ensure a balance between clean versus contaminated repairs in the two patient groups; and*

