The trial will be placed on hold based on the occurrence of the following serious adverse events: Death or Serious Infections, defined as any infection Grade ≥ 3 (as defined below). The DSMB shall review safety data once every nine to 12 months during planned DSMB Data Review Meetings. Data for the planned safety reviews will include, at a minimum, a listing of all reported adverse and serious adverse events. The DSMB will be informed of an Expedited Safety Report in a timely manner. In consultation with [name] we are planning that the DSMB will meet at least yearly to review study progress, accrual, data quality, and safety. Further, we plan a single interim analysis for efficacy and possible futility. This will be at the time the primary outcome can be assessed on half of the planned participants (50% information). Efficacy information will be presented between the arms in a semi-blinded fashion (e.g., arm A v. arm B). Efficacy will be based on a Lan DeMets continuous alpha spending approach with an O'Brien Fleming use function. Futility will use conditional power to assess the ability to reach a definitive conclusion. If the conditional power at 50% information to reject the original alternative hypothesis falls below 0.25, the board should consider the study futile.

In addition, the DSMB may be called upon for *ad hoc* reviews. The DSMB will review any event that potentially impacts safety at the request of the PI or Designated Safety Officer. If the DSMB or the PI determines that an unanticipated adverse device effect presents an unreasonable risk to subjects, they shall terminate all investigations or parts of investigations presenting that risk as soon as possible. Termination shall occur not later than 5 working days after this determination is made by the DSMB or the PI and not later than 15 working days after the DSMB and the PI first received notice of the effect.

The DSMB will report to the sponsor-investigator (in this case, the PI) any noncompliance with the signed Investigator's Agreement, conditions imposed by the IRB or FDA, and the requirements of the IDE.

The PI shall immediately conduct an evaluation of any unanticipated adverse device effects. Adverse effects will be graded by the PI and the attribution will ultimately be determined by the IRC.

The PI may not resume a terminated investigation without IRB and FDA approval.

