Clean wounds. Published data from our medical center noted an overall hernia recurrence rate of about 20% in predominantly clean wounds [43]. Similarly, our most recent retrospective analysis indicated hernia recurrence rates of 20%-30% and 50%-60% using synthetic versus biologic mesh, respectively, regardless of wound contamination (submitted for publication). Consequently, the power analysis for ventral hernia repairs under clean conditions indicates the need for 80 patients in each group, assuming a two-sided 0.05 level test and 80% power, and hernia recurrence rates of 40% versus 20% for patients receiving biologic versus synthetic prosthetics, respectively. The estimated recurrence rate of 40% with biologic mesh is consistent with estimates from the current medical literature [32].

Contaminated wounds. If we continue to assume a two-sided 0.05 level test and 80% power, and increase the estimated hernia recurrence rate from 40% to 60% for biologic prosthetics and from 20% to 30% for synthetic prosthetics used under contaminated conditions, then we will need to enroll a total of 40 patients in each group.

In total, we plan to enroll 250 patients to account for an anticipated drop out rate of <5% (**Table 2**). It is anticipated that approximately 40-45 patients will enroll in each of the study's next two (2) years. The nine active clinicians participating the trial perform approximately 175-200 open ventral hernia repairs per year. This enrollment target should guarantee that our study is adequately powered to demonstrate a significant difference in hernia recurrence rates, if present. Importantly, we have already demonstrated the ability to randomize ventral hernia repair patients to either treatment arm, a challenge that has effectively stymied other active studies (NCT02451176).

	Assumed recurrence rate for synthetic-mesh repairs	Assumed recurrence rate for biologic-mesh repairs	Required Sample Size for both groups (N_T)
Clean wounds	20%	40%	160
Contaminated wounds	30%	60%	80

Table 2. Power analysis.

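### The futility rule names the alternative, not the null, as the hypothesis to be rejected, and does not say which of the SAP's two design effects, or which trial total, it uses

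*Protocol*

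**What the plan says.** The Protocol's Data and Safety Monitoring Plan (Study Stopping Rules) plans one interim analysis, for efficacy and possible futility, at 50% information. Efficacy uses Lan-DeMets spending with an O'Brien-Fleming function. For futility it first gives the purpose: "Futility will use conditional power to assess the ability to reach a definitive conclusion". It then gives the criterion: "If the conditional power at 50% information to reject the original alternative hypothesis falls below 0.25, the board should consider the study futile".

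The aim is set in General study design: "A permanent synthetic prosthetic will be compared to a biologic prosthetic for clinical superiority". The same monitoring plan says of the board: "All DSMB members will review the protocol and ensure its understanding".

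The SAP has no interim or futility text. Its Power Analysis says "we performed separate power analyses for hernia repairs under clean versus contaminated wound conditions". For clean wounds it assumes "hernia recurrence rates of 40% versus 20% for patients receiving biologic versus synthetic prosthetics", with 80 per group. For contaminated wounds it proposes to "increase the estimated hernia recurrence rate from 40% to 60% for biologic prosthetics and from 20% to 30% for synthetic prosthetics", with 40 per group. No combined effect is stated. The SAP plans 250 patients in total and the Protocol 330.

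**The concern.** There are two separate faults.

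**Hypothesis.** A superiority trial succeeds by rejecting the null. Its futility rule should flag a low chance of doing so. The sentence flags a low chance of rejecting the alternative, which is what a trial running to plan produces. No other statement in the two documents corrects it.

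**Design effect.** The phrase about the original alternative is singular, but the SAP has two alternatives. Conditional power under the design needs one drift, meaning the expected final Z under the assumed effect. The drift depends on the assumed rates and on the trial total, and neither is fixed for the whole trial. A board statistician who mends the first fault by inference must still choose these, possibly after interim results by arm are available.

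**Working it through.** **Inputs.** Information fraction t = 0.5 and threshold 0.25 (Protocol, monitoring plan). Rates 40/20 and 60/30 with 80 and 40 per group, two-sided 0.05, 80% power (SAP, Power Analysis). Totals 250 (SAP) and 330 (Protocol), taken as 125 and 165 per arm. Positive Z favours synthetic.

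**Assumptions.** Normal approximation with unpooled variance; final critical value 1.96; and a 2:1 clean-to-contaminated mix taken from the 160:80 split in Table 2. The mix gives (80 × 0.40 + 40 × 0.60)/120 = 46.7% biologic and (80 × 0.20 + 40 × 0.30)/120 = 23.3% synthetic.

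**1. The SAP's sample sizes reproduce.** n = (1.96 + 0.8416)² × [p1(1-p1) + p2(1-p2)]/(p1-p2)².
- Clean: 7.849 × 0.40/0.04 = 78.5, so 79 (stated 80).
- Contaminated: 7.849 × 0.45/0.09 = 39.2, so 40 (stated 40).

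**2. Drift for one overall comparison, 125 per arm.** D = (p1-p2)/sqrt{[p1(1-p1) + p2(1-p2)]/n}.
- 40/20: 0.20/sqrt(0.40/125) = 3.54
- 60/30: 0.30/sqrt(0.45/125) = 5.00
- Mix: 0.2333/sqrt(0.4278/125) = 3.99

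**3. Corrected rule.** Conditional power to reject the null is Phi[(sqrt(t) z + (1-t)D - 1.96)/sqrt(1-t)]. Setting it to 0.25 gives z = (1.96 - 0.6745 × 0.7071 - 0.5D)/0.7071.

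| Alternative | D | Flag if Z below | Conditional power at Z = 0 | At Z = -0.8 | Flagged if no true difference |
|---|---|---|---|---|---|
| 40 v 20 | 3.54 | -0.40 | 0.39 | 0.14 | 34% |
| 60 v 30 | 5.00 | -1.44 | 0.78 | 0.49 | 8% |
| Mix 46.7 v 23.3 | 3.99 | -0.72 | 0.52 | 0.23 | 24% |

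The last column is Phi(flag). At the look, with 62.5 per arm and an average rate of 35%, the standard error of the difference is sqrt(2 × 0.35 × 0.65/62.5) = 0.085. The three flags are therefore observed differences of about 3, 12 and 6 points against synthetic. A Lan-DeMets final critical value of about 1.969 raises each flag by only about 0.01.

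**4. Effect of the total.** With 165 per arm the mix has D = 0.2333/sqrt(0.4278/165) = 4.58 and its flag is -1.14, against -0.72 with 125 per arm. At Z = -0.8 conditional power becomes 0.37, no longer futile. With the 120 per arm of Table 2 the mixed flag is -0.67.

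**5. Log-rank scale.** The SAP compares recurrence over time by log-rank test. Assuming proportional hazards, the hazard ratios are ln 0.8/ln 0.6 = 0.44 and ln 0.7/ln 0.4 = 0.39. With 35% events among 250 patients (87.5), the drifts sqrt(87.5/4) × -ln(HR) are 3.87 and 4.41, and the flags (critical value 1.969) are -0.63 and -1.01. The gap is smaller, but Z = -0.8 still falls between them.

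**6. The sentence read literally (illustration only).** Suppose the alternative is rejected when the final Z is below D - 1.96, a test that the documents do not define. Under the mix with 125 per arm, an interim result exactly on the design effect is Z = 0.7071 × 3.99 = 2.82. The literal value is Phi[(3.99 - 1.96 - 0.7071 × 2.82 - 0.5 × 3.99)/0.7071] = 0.003, which is below 0.25. Conditional power to reject the null at that point is 0.998.

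**The case against.** The preceding sentence describes futility as the ability to reach a definitive conclusion. In a superiority trial that points to rejecting the null, and a board statistician would very probably read it so. The rule is advisory, and the DSMB charter, which is not among these documents, may define the calculation. All of this stands and limits the severity.

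A reader might infer that the board would stop a trial that is going well. The documents do not support that: step 6 needs a test of the alternative that appears nowhere in the plan, so it shows only which way the wording points.

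A reader might also infer that the rule applies within each wound stratum, because the power analyses were separate. Each stratum at its own planned size has D = 2.83, which would put the flag at Z < 0.10 for both. But the SAP sets one primary comparison between the two treatment groups and treats clean versus contaminated as a subgroup question, and the Protocol plans a single look at half of all participants. These point to one whole-trial rule, so the per-stratum cut-off is not a main reason for the change.

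The objection leaves one gap. Recovering the intended hypothesis does not supply the effect or the total.

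**Conclusion.** The sentence is wrong as written, and it is incomplete once corrected. The hypothesis error is a drafting slip whose intent can be recovered. The unnamed alternative has practical effect: for one overall comparison with 125 per arm the flag lies anywhere from about -0.40 to -1.44, and the same interim Z of -0.8 gives opposite advice under 40/20 and 60/30. The unreconciled total moves the mixed-rate flag by a further 0.42.

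The harm after correction is small: under the mix with 125 per arm, the chance of a flag when the design effect is true is Phi(-0.72 - 0.7071 × 3.99), about 0.02%. The sizes rest on the normal approximation and the assumed 2:1 mix, and the gap between the two alternatives narrows on the log-rank scale. Severity is minor to should-fix.

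**What to change.** Replace the criterion with: *If conditional power to reject the null hypothesis at the final analysis, computed under the original design alternative, falls below 0.25, the board should consider the study futile (non-binding).*

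Add one clause that:
- says the rule applies to the whole trial;
- names the alternative, for example the Table 2 stratum rates combined;
- states the planned total used for the drift, once the Protocol's 330 and the SAP's 250 have been reconciled. The same total settles when half of the participants is reached (165 or 125).

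Make the change before the interim look, and repeat it in the SAP, which has no interim text. The cost is one sentence and one clause, with no extra patients, visits or analyses. The 0.25 threshold and the 50% look are unchanged.
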